1. OBJECTIVES

1.1 Primary Objectives

- 1.1.1 **Primary Objective in phase I portion of study:** To determine if the combination of nivolumab and a CCR2/CCR5 dual antagonist with GVAX is safe in patients with locally advanced pancreatic cancer (LAPC) who have received chemotherapy and radiotherapy.
- 1.1.2 **Primary Objective in phase II portion of study:** To determine if the combination of nivolumab and a CCR2/CCR5 dual antagonist with or without GVAX in patients with locally advanced pancreatic cancer (LAPC) who have received chemotherapy and radiotherapy enhances the infiltration of CD8+CD137+ cells in PDACs by comparing pre- and post-radiotherapy and immunotherapy treatment biopsies.

1.2 Secondary Objectives

- 1.2.1 **Secondary Objective in phase II portion of study:** To determine if the combination of nivolumab and a CCR2/CCR5 dual antagonist with or without GVAX is safe in patients with LAPC who have received chemotherapy and radiotherapy.
- 1.2.2 To determine the overall survival (OS) of patients with LAPC treated with chemotherapy and radiotherapy who subsequently receive nivolumab and a CCR2/CCR5 dual antagonist with or without GVAX compared to historical controls of patients treated with chemotherapy and radiation only and/or treated with GVAX plus anti-PD-1 antibodies.
- 1.2.3 To determine the metastasis free survival (MFS) of patients with LAPC treated with chemotherapy and radiotherapy who subsequently receive nivolumab and a CCR2/CCR5 dual antagonist with or without GVAX compared to historical controls of patients treated with chemotherapy and radiation only and/or treated with GVAX plus anti-PD-1 antibodies.
- 1.2.4 To determine the local progression free survival (LPFS) of patients with LAPC treated with chemotherapy and radiotherapy who subsequently receive nivolumab and a CCR2/CCR5 dual antagonist with or without GVAX compared to historical controls of patients treated with chemotherapy and radiation only and/or treated with GVAX plus anti-PD-1 antibodies.
- 1.2.5 To assess the surgical resectability rate of LAPC in subjects treated with chemotherapy and radiotherapy who subsequently receive nivolumab and a CCR2/CCR5 dual antagonist with or without GVAX compared to historical

A Phase I/II trial of combination immunotherapy with nivolumab and a CCR2/CCR5 dual antagonist (BMS-813160) with or without GVAX following chemotherapy and radiotherapy for locally advanced pancreatic ductal adenocarcinomas (PDACs)

controls of patients treated with chemotherapy and radiation only and/or treated with GVAX plus anti-PD-1 antibodies.

- 1.2.6 To assess the pathological response rate of subjects with LAPC in subjects treated with chemotherapy and radiotherapy who subsequently receive nivolumab and a CCR2/CCR5 dual antagonist with or without GVAX compared to historical controls of patients treated with chemotherapy and radiation only and/or treated with GVAX plus anti-PD-1 antibodies.

1.3 Exploratory Objectives

- 1.3.1 To evaluate the quality of life of subjects with LAPC in subjects treated with chemotherapy and radiotherapy who subsequently receive nivolumab and a CCR2/CCR5 dual antagonist with or without GVAX compared to historical controls of patients treated with chemotherapy and radiation only and/or treated with GVAX plus anti-PD-1 antibodies.
- 1.3.2 To evaluate the effects of the combination of nivolumab and a CCR2/CCR5 dual antagonist with or without GVAX and standard multimodality treatments upon the activation and expansion of T effector cells (Teffs) infiltrating into the tumor microenvironment (TME) compared to historical data of the TME in PDACs of patients treated with GVAX and nivolumab, and of patients treated with standard chemotherapy and SBRT.
- 1.3.3 To evaluate the tumor immune infiltrate [including tumor-associated macrophages (TAMs), myeloid-derived suppressor cells (MDSC), regulatory T-cells (Treg), CD4+OX40+, CD8+OX40+ cells] response after treatment with nivolumab and CCR2/CCR5 dual antagonist with or without GVAX and standard multimodality treatments compared to historical data of the TME in PDACs of patients treated with GVAX and nivolumab, and of patients treated with standard chemotherapy and SBRT.
- 1.3.4 To evaluate the immune parameters relevant to the activation of PD-L1/PD-1 associated immunosuppressive pathways, CCR2/CCR5/CXCR4 associated myeloid cell pathways and vaccine-induced immune regulatory signatures after treatment with nivolumab and CCR2/CCR5 dual antagonist with or without GVAX and standard multimodality treatments compared to historical data of the TME in PDACs of patients treated with GVAX and nivolumab, and of patients treated with standard chemotherapy and SBRT.
- 1.3.5 To evaluate mutated neoepitope specific T cell repertoire in pre- and post-treatment tumor specimens and in peripheral blood lymphocytes over time on treatment.

A Phase I/II trial of combination immunotherapy with nivolumab and a CCR2/CCR5 dual antagonist (BMS-813160) with or without GVAX following chemotherapy and radiotherapy for locally advanced pancreatic ductal adenocarcinomas (PDACs)

- 1.3.6. To monitor the peripheral and intratumoral antigen-specific T-cell responses after treatment with nivolumab and CCR2/CCR5 dual antagonist with or without GVAX and standard multimodality treatments.
- 1.3.7 To assess tumor tissue for molecular determinants of response, progression and disease stability using next generation sequencing technology.
- 1.3.8 To assess tumor burden dynamics using both standard protein biomarkers such as CA19-9 and other exploratory circulating biomarkers in serial collections of sera and plasma at baseline and throughout treatment.
- 1.3.9 To assess the baseline characteristic of the subjects enrolled and to correlate these molecular and clinicopathologic criteria with treatment response and toxicity. DNA will be extracted from whole blood and used to evaluate for any germline mutations, which may correlate with response or toxicity.
- 1.3.10 To collect peripheral blood lymphocytes to explore the association of PD-1 positivity and lymphocyte activation markers with clinical responses.

1.4 Primary Endpoints

1.4.1 Primary Endpoint in phase I portion of study: Safety

- Study-related adverse events according to National Cancer Institute Common Toxicity Criteria for Adverse Events (NCI CTCAE; Version 5.0) that occur on or after Cycle 1, Day 1 immunotherapy.
- Incidence, nature and severity of all adverse events that occur on or after Cycle 1, Day 1.

1.4.2 Primary Endpoint in phase II portion of study: Immunologic

- Immune response, defined as >80% increase of infiltration of CD8+CD137+ T cell density after the first immunotherapy cycle (at the time of surgery or surgical evaluation if not a candidate) compared to baseline (prior to SBRT and after chemotherapy).
- Multiplex IHC staining of CD8+CD137+ cells in formalin-fixed, paraffin-embedded (FFPE) tissue slides of pre- and post-immunotherapy treatment PDAC biopsies. This will be analyzed by the Perkin-Elmer-Vectra multiplex immunofluorescent staining method.

1.5 Secondary Endpoints

1.5.1 Secondary Endpoint in phase II portion of study: Safety

- Study-related adverse events according to National Cancer Institute Common Toxicity Criteria for Adverse Events (NCI CTCAE; Version 5.0) that occur on or after Cycle 1, Day 1 immunotherapy.

A Phase I/II trial of combination immunotherapy with nivolumab and a CCR2/CCR5 dual antagonist (BMS-813160) with or without GVAX following chemotherapy and radiotherapy for locally advanced pancreatic ductal adenocarcinomas (PDACs)

- Incidence, nature and severity of all adverse events that occur on or after Cycle 1, Day 1.

1.5.1 Efficacy Endpoints

- OS from the time of Cycle 1, Day 1 of immunotherapy until death from any cause.
- MFS from the time of Cycle 1, Day 1 of immunotherapy until first documented distant metastases on imaging or death, whichever occurs first.
- LPFS from the time of Cycle 1, Day 1 of immunotherapy until first documented local progression on imaging or death, whichever occurs first.
- Surgical resectability determined by successful performance of resection (as defined by R0 and R1 resection).
- Pathologic response as determined by surgical margins and residual disease.

1.6 Exploratory/Correlative Endpoints

- Quality of life will be evaluated using the EORTC QLQ-C30/Pan26 questionnaire.
- Evaluate changes in CD4+OX40+ and CD8+OX40+ cell density in pre- and post-treatment specimens via Halo-analysis.
- Evaluate changes in the expression of CCR2, CCR5, CXCR4 and PD-L1/PD-1 pathways in pre- and post-treatment specimens by nanostring analysis.
- Evaluate changes in M1 vs. M2 TAM, Teff:Treg, and MDSC by multiplex IHC.
- Evaluate mutated neoepitope specific T cell repertoire by TCR clonality and/or the MANAFEST assay in pre- and post-treatment tumor specimens and in peripheral blood lymphocytes over time on treatment.
- Cytokine/chemokine assays to assess changes in intratumoral inflammatory markers
- Peripheral antigen specific T-cell responses
- Intratumoral antigen specific T-cell responses
- Biomarker marker changes (including standard protein biomarkers such as CA 19-9) and correlation to evaluate for prognostic or predictive factors
- To assess correlation between immune parameters and clinical outcomes using univariate and multivariate Cox regression models

1.7 Study Design

This is a single-center, open label, phase I/II clinical trial to evaluate the immune effects, safety and clinical activity of the combination of nivolumab and CCR2/CCR5 dual antagonist with or without GVAX in patients who have received standard chemotherapy and stereotactic body radiation therapy (SBRT) for LAPC.

Patients who have a new diagnosis of untreated LAPC will be eligible for enrollment. We will consent patients at the time of diagnosis of LAPC based upon criteria from NCCN Guidelines as determined by review of imaging and pathology at our institution. If the patient has not had a diagnostic core biopsy adequate for review by our institution, an on-study core diagnostic biopsy will be performed. If the patient's available imaging is not adequate for review by our institution, repeat imaging will be performed. The patient will also undergo blood draws at the time of screening and enrollment. After completing all screening procedures and meeting eligibility criteria, the patients will then receive FOLFIRINOX-based induction chemotherapy and SBRT. Chemotherapy and radiotherapy are considered standard therapy. Chemotherapy may be administered at any facility, but SBRT treatment will be performed at Johns Hopkins. Of note, patients should meet all eligibility criteria and have all screening procedures completed prior to initiating chemotherapy, however they may be enrolled up to one month after beginning SOC chemotherapy to allow for time to collect records from outside institutions if necessary. Only toxicities considered related to study procedures or treatment will be collected during this period. The patients should receive at least eight and no more than sixteen 14-day cycles of FOLFIRINOX-based chemotherapy. After completion of chemotherapy, the patients will undergo EUS-guided fiducial placement along with a post-chemotherapy core biopsy of the pancreas tumor, blood draws to evaluate for circulating tumor cells and other inflammatory markers and an SBRT simulation. We will not confirm presence of tumor in the post-chemotherapy core biopsy since some patients may not have persisting tumor; the biopsy is to evaluate the tumor microenvironment. SBRT will be initiated (6.6 Gy x 5 days) approximately two to four weeks after completion of chemotherapy.

After completion of SBRT, the patients will then be re-evaluated for eligibility for continuation in the study and must have LAPC based on NCCN Guidelines as determined by review of CT, PET, or MRI imaging at our institution. Patients who have developed metastatic disease are no longer eligible to continue in the study. If the patients remain eligible for continuation in the study after rescreening, they will be assigned or randomized to a study arm (depending on when they were enrolled).

Due to availability of BMS-813160, study enrollment was closed as of December 19, 2022. Patients randomized prior to this will continue receiving study treatment as planned until drug supply expires on July 31, 2023, then will continue to receive any remaining study cycles without BMS-813160. Any patients who were enrolled but not randomized prior to December 19, 2022 (i.e. those receiving chemotherapy) will be assigned to a new arm (Arm C).

In phase I, the combination immunotherapy consists of nivolumab, CCR2/CCR5 dual-antagonist (BMS-813160) and GVAX. In phase II, the first 10 patients will be randomized 1:1 between Arm A and Arm B. Remaining patients will be assigned to Arm C.

Arm A subjects receive nivolumab and BMS-813160, Arm B subjects receive nivolumab, BMS-813160, and GVAX, and Arm C patients will receive nivolumab and BMS-813160 for Cycle 1 (prior to surgery) and then nivolumab and GVAX for Cycles 2 and beyond.

After randomization or assignment to a study arm, subject will receive Cycle 1 of the combination immunotherapy. Cycle 1 lasts 28 days and will start within two weeks of completion of SBRT.

Surgery will be scheduled to occur between five to seven weeks after completion of SBRT. If surgery is scheduled more than 28 days from the start of Cycle 1, anti-CCR2/5 therapy will be continued up to the day before surgery (but a second dose of nivolumab and GVAX will not be administered because this is not considered a new cycle). Standard surgical procedure will be determined by the operating surgeon. Surgery is considered standard of care and must be performed at Johns Hopkins. Only toxicities considered related to study procedures or treatment will be collected from the time of surgery until the start of Cycle 2. Post-treatment biospecimens will be obtained intraoperatively for resectable patients. If the patient is found to have an unresectable tumor during surgery, research core biopsies will be obtained intraoperatively. For patients who are not surgical candidates, they will undergo an EUS-guided tumor biopsy.

Both resected (estimated 30-40%) and unresected patients will receive combination immunotherapy every 28 days for a total of 4 more cycles or until the development of metastatic disease. For those who undergo a surgery or NanoKnife procedure, immunotherapy will be initiated within 6 to 12 weeks of the procedure. For those who are not surgical candidates, the immunotherapy will not be held. Patients with local progression will be allowed to continue the study treatment. Participants who develop metastatic disease after the initiation of immunotherapy will go off trial, but they will be offered biopsy of the metastatic lesions if they can be safely biopsied (as determined by our interventional radiology team). Patients will be expected to be on trial for approximately 7 to 9 months if they undergo surgery, and approximately 6 months if they do not undergo surgery.

Following the 4 cycles of immunotherapy post-surgical evaluation, if the patient remains free of metastatic disease, the patient will have the option of receiving maintenance immunotherapy. During the maintenance portion of the study, Phase I or Phase II Arm B patients will receive BMS-813160 given bi-daily for 24 weeks, nivolumab every 4 weeks for a total of six 28-day cycles, and GVAX given once on Cycle 1 Day 2. Phase II Arm A patients will receive BMS-813160 bi-daily for 24 weeks, and nivolumab every 4 weeks for a total of six 28-day cycles. Phase II Arm C patients will receive nivolumab every 4 weeks for a total of six 28-day cycles, and GVAX once on Cycle 1 Day 2.

The primary endpoint of Phase I is safety, and the primary endpoint of Phase II is the degree of CD8+CD137+ T-cells infiltration in pre- and post-immunotherapy tumor specimens. Individuals will be censored at the date of last scan if no event has occurred. Secondary endpoints are OS, MFS, LPFS, surgical resectability, and pathologic response and as defined above. Exploratory endpoints include quality of life and immunologic, genetic/molecular and biomarker analysis, some of which will be correlated with clinical outcomes.

The Phase I portion is a 3+3 dose-escalation design to determine the maximum tolerated dose (MTD) or recommended phase 2 dose of BMS-813160 for use in the combination. It will evaluate two dose levels and enroll 3 to 12 patients depending on the number of dose limiting toxicities (DLT). All patients in Phase I portion will receive nivolumab, CCR2/CCR5 dual-antagonist (BMS-813160) and GVAX. DLT evaluation interval is the first cycle of treatment, beginning on the first day of treatment.

The MTD will be determined using the following escalation rules:

- A cohort of three patients will be entered at each dose level.
- If none of the subjects has a DLT during their first cycle, then the dose will be escalated and subjects will be enrolled at the next dose level.
- If 1 of 3 subjects at a given dose level has a DLT during the first cycle, then 3 additional subjects will be enrolled at the same dose level. Dose escalation will only occur if no additional DLTs are observed in the 3 additional subjects after they have been followed for one cycle of treatment.
- If 2 or more subjects at a dose level have a DLT during the first cycle, dose escalation will cease, and this dose level will have exceeded the MTD. New subjects will be enrolled at next lower dose level until that cohort has 6 subjects.
- A total of 6 patients must be enrolled at a dose level in order to declare MTD.
- The MTD will be defined as the dose of BMS-813160 in the combination in which < 2 of 6 patients experiences a DLT with the next higher dose having at least 2 of 3 or 2 of up to 6 patients experiencing a DLT.
- If ≤ 1 in 6 patients experience DLT at dose level 2, dose escalation will stop and this dose level will be the recommended dose for Phase II.

The Phase II portion is a randomized two-arm study to evaluate immune response, efficacy and safety of the combination of nivolumab and CCR2/CCR5 dual-antagonist (BMS-813160) with and without GVAX. We will be monitoring the toxicities for each arm in the Phase II portion, and if we observe >33% unacceptable toxicities in the first 6 patients or any time afterwards in any arm, we will halt the enrollment pending safety evaluations.

DLTs will be assessed in the first cycle of Phase I, starting Cycle 1 Day 1 through prior to initiation of Cycle 2. Unacceptable toxicities will be used to monitor safety from Cycle 2 Day 1 of Phase I through to end of study treatment and from Cycle 1 Day 1 of Phase II through to end of treatment. During periods of standard of care treatment (FOLFIRINOX-based chemotherapy, SBRT, Surgery) only AEs considered related to study treatment will be collected. If patients develop adverse events (AEs) to any of the three immunotherapies

A Phase I/II trial of combination immunotherapy with nivolumab and a CCR2/CCR5 dual antagonist (BMS-813160) with or without GVAX following chemotherapy and radiotherapy for locally advanced pancreatic ductal adenocarcinomas (PDACs)

(BMS-813160, nivolumab or GVAX) leading to its/their discontinuation, they will be taken off the trial.

All patients will undergo standard of care evaluations consisting of history and physical, CT of the chest/abdomen/pelvis or MRI abd/pelvis and non-contrast CT chest (if do not tolerate contrast) to evaluate for local progression and metastatic disease while they are on study.

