5.1 Dose Delays

All scheduled cycles within a course are to be given approximately four weeks apart. If necessary, a cycle may be delayed for up to one week, and subsequent cycles should continue to be four weeks apart. If delayed more than one week, the Principal Investigator must be contacted for further instructions on continued treatment. Additional delays or modifications to the treatment schedule must be approved by the Principal Investigator or IND Sponsor.

A Phase I/II trial of combination immunotherapy with nivolumab and a CCR2/CCR5 dual antagonist (BMS-813160) with or without GVAX following chemotherapy and radiotherapy for locally advanced pancreatic ductal adenocarcinomas (PDACs)

If a delay occurs between Day 1 and 2 of a cycle:

- Nivolumab-related infusion reactions must resolve to baseline prior to administration of GVAX and BMS-813160.
- GVAX and BMS-813160 treatment and assessments can be resumed after the reason for delay has resolved.

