12.7 Exploratory Analysis – Quality of Life

Quality of life will be assessed via EORTC QLQ-C30/Pan26 (v3.0) questionnaire. Our study population is pancreatic cancer subjects, and the analysis will be focused on Global Health Status/QoL scale, symptom scale (fatigue, pain), and functional scale (physical functioning, role functioning, emotional functioning) comparing data from initial enrollment into study and as per study calendar (**Section 9**). For each module, summary statistics of the score will be reported as baseline and follow up time. Changes of quality of life score before and after treatment will be tested via paired t-test. In addition, mixed effect models will be fitted for assessing the pattern of quality of life over time. The frequency and proportion of patients who reach minimal clinically important difference (MCID) of 10-points change from baseline will be tabulated by time. Logistic mixed effects models will be used to track the proportion over time. The time to definitive deterioration in quality of life, defined as a decline of 10 points or more, will be analyzed using the Kaplan Meier method.

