Comparison in pre- and post-treatment biomarker data will be compared using paired t-tests (or Wilcoxon signed rank tests if appropriate) and McNemar's tests for dichotomous or categorical variables. Associations between immune parameters will be explored graphically (e.g. scatterplots, boxplots) and numerically (e.g. correlations, Fisher's exact tests). Mixed effects models will be used to assess the patterns in biomarkers over time.

Efficacy measures will include OS, MFS, LPFS, surgical resectability and pathologic response. Demographic and case-history factors will be examined to determine whether stratification or adjustments should be made within the subsequent statistical analyses, and if necessary, the appropriate stratification or adjustment will be made. Biomarkers will be summarized graphically as they relate to efficacy and safety endpoints, as applicable. Summary statistics will be tabulated. The relationships between binary measures (e.g. response) and time to event outcomes (e.g. OS) and candidate biomarkers will be investigated using logistic regression and Cox proportional hazards regression, respectively. Associations will be summarized in terms of point and interval estimates of hazard ratios, odds ratios, or other statistics, as appropriate for the analyses completed. Models to predict clinical activity based on combinations of biomarkers may also be investigated.

REFERENCES

2. Ahlgren JD. Epidemiology and risk factors in pancreatic cancer. *Semin Oncol*. 1996;23(2): 241-50.
3. Loehrer PJ, Sr., Feng Y, Cardenes H, et al. Gemcitabine alone versus gemcitabine plus radiotherapy in patients with locally advanced pancreatic cancer: an Eastern Cooperative Oncology Group trial. *J Clin Oncol*. 2011;29(31): 4105-12.

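### Exploratory quality-of-life and blood-marker analyses: from Cycle 2 Day 1 on, operated and non-operated patients are measured at different times and in different clinical states, and the plan does not separate them

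*Combined protocol and SAP*

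**What the plan says.** **Timing.** Section 1.7 sets the start of immunotherapy ("Cycle 1 lasts 28 days and will start within two weeks of completion of SBRT") and the date of surgery ("Surgery will be scheduled to occur between five to seven weeks after completion of SBRT") on the same clock. After a procedure, "For those who undergo a surgery or NanoKnife procedure, immunotherapy will be initiated within 6 to 12 weeks of the procedure". For the rest, "For those who are not surgical candidates, the immunotherapy will not be held". Section 5.1 adds that "a cycle may be delayed for up to one week, and subsequent cycles should continue to be four weeks apart".

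**Collection.** Section 9 uses one post-surgical calendar for both kinds of patient. It marks research blood, serum and plasma at C2D1 and end of treatment, CA 19-9 on Day 1 of every cycle, and the QoL questionnaire at C2D1, C4D1 and end of treatment. The pre-surgical calendar marks all of these at C1D1 and again at an End of Cycle 1 visit. That visit is set for C1D28, or for the eve of surgery if that is earlier, with a window of -3/+14 days.

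**Analysis.** Section 12.7: "Changes of quality of life score before and after treatment will be tested via paired t-test". It also plans mixed models over time, the proportion of patients with a 10-point change from baseline, and a Kaplan-Meier analysis of time to definitive deterioration. Section 12.8 plans paired tests of pre- against post-treatment values and adds: "Mixed effects models will be used to assess the patterns in biomarkers over time". Neither section says which visit is the post-treatment one. Neither names surgery or NanoKnife as a stratum, reporting group or censoring event.

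**The concern.** C2D1 has one label but means two different things. In an operated patient it comes 6–12 weeks after a pancreatic procedure. BMS-813160 stopped the day before surgery, and the only nivolumab dose was given 9–19 weeks earlier. If the tumour was resected, the primary is gone. In a patient who is not a surgical candidate, C2D1 follows directly on Cycle 1 with treatment not held.

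An analysis that pools the two from C2D1 on mixes post-operative values with on-treatment values. A drop in QoL during surgical recovery would count towards the 10-point decline and towards deterioration. A fall in CA 19-9 after resection would enter the same average as a fall under drug. Nothing in the analysis as written would let a reader tell these apart.

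**Working it through.** **Inputs** (sections 1.7, 4.10, 5.1, 9 and 12.2)
- C1D1: 0–2 weeks after SBRT
- Surgery: 5–7 weeks after SBRT
- Cycle 2 after a procedure: 6–12 weeks
- Cycle 2 without a procedure: no hold, so 4 weeks after C1D1, plus a 1-week window
- Cycles 2–5: 4 × 4 = 16 weeks; end-of-treatment visit 30 days (4.3 weeks) after the last dose
- Expected resected: 30–40%; analysis groups of about 8–10 patients

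**1. Timing of C2D1, in weeks after C1D1**
- Surgery: 5 − 2 = 3 to 7 − 0 = 7
- C2D1, operated: 3 + 6 = 9 to 7 + 12 = 19 (up to 20 if the +7-day window is added)
- C2D1, not operated: 4 to 4 + 1 = 5
- Difference: 9 − 5 = 4 to 19 − 4 = 15

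These are the corners of the permitted windows, not expected averages.

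**2. Check against the plan's own figure.** Section 1.7 expects about 7 to 9 months on trial with surgery and about 6 without.
- Operated: 9 + 16 + 4.3 = 29.3 to 19 + 16 + 4.3 = 39.3 weeks, or 6.7–9.0 months
- Not operated: 4 + 16 + 4.3 = 24.3 to 5 + 16 + 4.3 = 25.3 weeks, or 5.6–5.8 months

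The intervals reproduce the stated durations, so they are being read as the plan intends.

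**3. Later visits.** Cycles stay four weeks apart, so the shift carries forward.

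| Visit | Operated (weeks after C1D1) | Not operated |
|---|---|---|
| C2D1 | 9–19 | 4–5 |
| C4D1 (+8) | 17–27 | 12–13 |
| C5D1 (+12) | 21–31 | 16–17 |

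**4. Is there a visit free of surgery?** Yes. End of Cycle 1 is set before surgery and carries QoL, CA 19-9 and research blood. But surgery can come as early as 3 weeks after C1D1, and the visit may run 14 days late. A measurement inside the window can therefore still be post-operative.

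**5. Illustration of size.** The documents give no surgical effect on any of these measures, so the effects below are assumptions. The shift in a pooled mean is the operated share times the surgical effect. At a share of 30–40%:
- 5 QoL points: 1.5–2 points
- 10 points: 3–4 points
- 20 points: 6–8 points

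The 30–40% is the resected share. If 50% had some procedure (assumed), a 10-point effect would shift the mean by 5 points.

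**6. Subgroup size.** 0.30 × 8 = 2.4 to 0.40 × 10 = 4, so about 2–4 resected patients per group.

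**The case against.** The case on the other side is substantial, and much of it stands.

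- **The objectives do not all ask for a drug effect.** Objective 1.3.8 concerns tumour burden, through "serial collections of sera and plasma at baseline and throughout treatment"; a fall in CA 19-9 after resection belongs to that picture. Objective 1.3.10 is about association. Objective 1.3.1 describes QoL on a pathway that includes planned surgery. A reader might infer that the plan credits surgical effects to the immunotherapy. It nowhere does so. The fault is only that the two cannot be told apart.
- **The pre-operative visit may already be the intended one.** Section 9 calls the visit just after C1D28 the post-immunotherapy evaluation, and section 8.2 uses that name for its blood draw. Section 12.8 ties post-treatment tissue to the resected or core biopsy sample and plans similar analyses in blood. A reader might infer that the paired tests are confounded by surgery. The documents show only that their post-treatment visit is unnamed, and for blood they lean towards the clean one.
- **Nominal visits are not prescribed.** Neither section says how time enters the models, so actual time is not excluded.
- **Some adjustment is foreseen.** Section 12.8 allows stratification or adjustment for demographic and case-history factors if needed, and relates markers to resectability. The adjustment is conditional and does not name surgery, and none of this reaches the QoL analyses in 12.7. It softens the point without answering it.
- **The endpoints are exploratory.** This is correct and limits the weight of the point.

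**Conclusion.** The point holds as an inexpensive improvement to exploratory analyses. C2D1 is at 9–19 weeks in operated patients and 4–5 weeks in the rest. These figures belong to C2D1 alone; later visits are later, with the same shift of about 4–15 weeks. As sections 12.7 and 12.8 stand, the over-time models pool the two kinds of patient, and 12.7 does so in the 10-point proportions and time to deterioration as well. From C2D1 on, procedure and immunotherapy cannot be separated in these results.

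The timing follows from the documents without further assumption. The size of any distortion does not; the QoL shifts above only illustrate scale.

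Two stronger inferences are not supported. The Phase II primary endpoint is not affected: its tissue is taken at surgery or surgical evaluation, before Cycle 2. Nor does the problem call for a model with a time-varying procedure term, which 2–4 resected patients per group could not estimate usefully.

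**What to change.** Change the wording of sections 12.7 and 12.8 in two places.

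1. **Name the contrast.** Make C1D1 to End of Cycle 1 the main pre/post comparison for QoL, CA 19-9 and blood markers. Exclude any End of Cycle 1 sample or questionnaire actually taken after the procedure.
2. **Separate later visits.** From C2D1 on, place each measurement at its actual number of weeks since C1D1. Report QoL (including the 10-point proportions and time to deterioration) and blood markers separately for three sets of patients: resected; other procedure (NanoKnife, or found unresectable at surgery); and not operated. Keep this descriptive, with no time-varying procedure term.

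The cost is analysis wording only. The measurements and the visit and procedure dates it needs come from visits and procedures already in the plan, and no visit, treatment or clinical rule changes. The price is that the clean contrast covers a single cycle, and the later subgroups will be too small for more than listing and plotting.
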